2 ACRONYMS AND ABBREVIATIONS

PI = Principal Investigator

Subject = Patient = Study Participant

RLS = Restless Legs Syndrome

IRLS = International Restless Legs Syndrome-Rating Scale

ASRS = Augmentation Severity Rating Scale

RLS-QOL = Restless legs Syndrome—Quality of Life

MOS-SS = Medical Outcome Study–Sleep Scale

DA = Dopaminergic Agents

SSRIs = Selective Serotonin Reuptake Inhibitors

CBC with differential = Complete Blood Count with differential

CMP = Comprehensive Metabolic Panel

FDA = Food and Drug Administration

3 STUDY FLOW CHART

	Pre-Rx 'Screening Phase' (duration	Baseline	Rx Phase 1		Rx Phase 2		
	= 15 days)	Day 0 +/-7	Day 30 +/-7	Day 90 +/-14	Day 120 +/-14	Day 180 +/-14	Day 360 +/-14
Enrolment Period	1 year						
Medical History**	X	X	X	X	X	X	X
Concomitant Medication(s)	X	X	X	X	X	X	X
Vital Signs	X	X	X	X	X	X	X
Physical Examination	X	X	X	X	X	X	X
ASRS(*)	X	X	X	X	X	X	X
IRLS(*)	X	X	X	X	X	X	X
RLS-QOL(*)		X	X	X	X	X	X
MOS-SS(+*)		X	X	X	X	X	X
CBC and differential, CMP	X		X				X
Monitoring & Recording of Adverse Events		X	X	X	X	X	X
Urine pregnancy analysis	X	X	X	X	X	X	X
Urine sample collection (drug screen)	X						
Serum pregnancy analysis Serum Ferritin Level	TBD	TBD	TBD	TBD	TBD	TBD	TBD

Rx Phase 1 (Day 0-90) = Stable DA + Horizant

Rx Phase 2 (Day 120-360) = DA taper/Horizant only

- + = Subjects will also be requested to keep a sleep diary.
- * = See attachments.
- ** = Medical history includes Interval history between clinic visits.

4. SUMMARY

Study Title: To examine the effect of Horizant (Gabapentin Enacarbil) in primary Restless legs syndrome (RLS) patients who are on dopaminergic agents and exhibiting augmentation.

Objectives:

The Primary objective: is to evaluate the efficacy of Dopamine combined therapy with addition of Horizant (600 mg, oral, once daily) for 90 days in the treatment of Augmentation.

The Secondary objectives: is to evaluate the efficacy of Horizant (600 mg, oral, once daily) alone with Dopaminergic (DA) taper for up to 270 days in the treatment of Augmentation.

Study Design:

This is an Open label single arm study. The purpose of the study is to demonstrate the efficacy of Horizant in patients with RLS who exhibit augmentation while on Dopaminergic therapy. Adult patients (age 18-85 years) with diagnosis of primary RLS (diagnosed by study investigators) with augmentation on dopaminergic therapy will be screened for participation in the study. RLS diagnosis will be made by the study investigators using International RLS study group criteria. Patients with augmentation on dopaminergic therapy as defined by NIH 2007 (refer to attachment) with ASRS of 5 to 15 will be offered to participate in the study. Inclusion and exclusion criteria are listed below. The study will be performed after approval of the Institutional Review Board of the University of Missouri.

A total of 50 subjects will be entered into the study over a period of 1 year. Written consent will be obtained from all patients. After pre-participation evaluation for eligibility, subjects will be selected and enrolled in the study and followed for a total of 6 follow up visits (Days 0, 30, 90, 120, 180, 360). Subjects Enrollment period will last up to 12 months. The total duration of study will be 24 months.

Pubmed search (using words Horizant, Augmentation) pulled out several articles (see attachments) indicating Horizant is the "only FDA approved Non-Dopaminergic Drug" used in the treatment of RLS. Its predictable bioavailability, acceptable safety profile and no case reports of augmentation after its use, in the literature makes Horizant the best-suited drug for conducting a clinical drug trial focused on examining its potential benefit in RLS patients who developed augmentation.

Abrupt withdrawal of DA agent can be potentially dangerous due to DA withdrawal symptoms including life-threatening Neuroleptic Malignant Syndrome. Therefore, Rx Phase 1 and Rx Phase are designed to help improve subject tolerability.

Therefore, during Rx Phase 1, Horizant (600 mg oral once daily at 5 pm) will be added on as an adjunct to all subjects' along with stable dose of their current dopaminergic (DA) agent and both medications will be continued for a total period of 90 days from day 0 to day 90.

At the 90th day follow-up visit, with initiation of Rx Phase 2, all subjects will be tapered off (by 50% reduction in dose each week) of their current dopaminergic agent while maintaining the same dose of Horizant and will be on Horizant monotherapy. All subjects will be followed for additional three follow up clinic visits (days 120, 180, 360).

During this period all subjects will be monitored for symptoms of dopamine withdrawal or worsening of RLS or emergence of other symptoms which will be managed clinically by physicians. All subjects will continue to be on Horizant for the entire duration of this study with close follow up. Of note, if deemed appropriate for reasons related to safety, tolerability, and continuation of the study, the PI, at his discretion, may modify the tapering schedule of the DA although every attempt will be made to adhere to the protocol specified schedule of DA tapering.

During each clinic visit all subjects will undergo careful evaluations (by a physician) that will include: medical history such as appearance of any new health problems, any new symptoms/adverse events between clinic visits, concomitant medication(s) history (medication reconciliation), physical examination with assessment of vital signs, ASRS, IRLS, RLS-QOL, and MOS-SS.

All subjects will undergo laboratory testing (CBC with Diff and CMP) during screening, on day 30 and day 360 (final clinic visit). In addition, urine sample will be collected at screen visit for illegal drug testing. Additional hematology and urine sample analysis for illegal drug will be performed as needed at the discretion of the investigators if an adverse event is reported by a subject. Serum Ferritin level will be performed as needed at the discretion of the investigators.

Urine pregnancy screening is required for all females of childbearing potential at screen and each clinical visits, if positive, serum pregnancy test will be performed. Female subjects who have undergone surgical sterilization, who are post-menopausal (defined as age >50 and >1 year of amenorrhea), who have medically documented ovarian failure (defined as age <50 with serum estradiol and follicle-stimulating hormone [FSH] levels within the institutional postmenopausal range and a negative serum or urine β HCG) do not need to undergo pregnancy screening.

At study completion, appropriate statistical analysis will be performed to evaluate the outcomes. We plan to publish the findings and results of this study.

Study Population:

Primary RLS patients who developed augmentation on DA therapy and score of 5 to 15 on ASRS scale.

We plan to recruit 50 patients; male and female, age 18-85 years.

Recruitment site is University of Missouri-Columbia. We may use advertisement(s) in the local media to recruit subjects.

Outcome Parameters/Evaluation:

The Primary outcome parameter:

- 1) A reduction in the Augmentation Severity Rating Scale (ASRS)
- 2) Improvement in the International Restless Legs Syndrome-Rating Scale (IRLS)
- 3) Improvement in the Restless Legs Syndrome-Quality of Life (RLS-QOL)
- 4) Improvement in the Medical Outcome Study-Sleep Scale (MOS-SS)

The Secondary outcome parameters:

- 1) A reduction in the Augmentation Severity Rating Scale (ASRS)
- 2) Improvement in the International Restless Legs Syndrome-Rating Scale (IRLS)
- 3) Improvement in the Restless Legs Syndrome-Quality of Life (RLS-QOL)
- 4) Improvement in the Medical Outcome Study-Sleep Scale (MOS-SS)

Treatment Group: This is a Single Arm study. All subjects will receive Horizant 600 mg once daily.

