The Primary objective: is to evaluate the efficacy of Dopamine combined therapy with addition of Horizant (600mg, oral, once daily) for 90 days in the treatment of Augmentation.

The Secondary objectives: is to evaluate the efficacy of Horizant (600 mg, oral, once daily) alone with Dopaminergic (DA) taper for up to 270 days in the treatment of Augmentation.

6.1 Study Design:

This is an Open label Single arm study. The purpose of the study is to demonstrate the efficacy of Horizant in patients with RLS who exhibit augmentation while on Dopaminergic therapy. Adult patients (age 18-85 years) with diagnosis of primary RLS (diagnosed by study investigators) with augmentation on dopaminergic therapy will be screened for participation in the study. RLS diagnosis will be made by the study investigators using International RLS study group criteria. Patients with augmentation on dopaminergic therapy as defined by NIH 2007 (refer to attachment) with ASRS of 5 to 15 will be offered to participate in the study. Inclusion and exclusion criteria are listed below. The study will be performed after approval of the Institutional Review Board of the University of Missouri.

A total of 50 subjects will be entered into the study over a period of 1 year. Written consent will be obtained from all patients. After pre-participation evaluation for eligibility, subjects will be selected and enrolled in the study and followed for a total of 6 follow up visits (Days 0, 30, 90, 120, 180, 360). Subjects Enrollment period will last up to 12 months. The total duration of study is 36 months.

There is no report of Augmentation due to Horizant use in the literature to this date. Therefore, initially Horizant (600 mg oral once daily at 5 pm) will be added on as an adjunct to all subjects' along with stable dose of their current dopaminergic (DA) agent and both medications will be continued for a total period of 90 days from day 0 to day 90.

At the 90th day follow-up visit, while maintaining the same dose of Horizant, all subjects will be tapered off (by 50% reduction in dose each week) of their current dopaminergic agent. Subsequently all subjects will be followed for additional three follow up clinic visits (days 120, 180, 360). During this period all subjects will be monitored for symptoms of dopamine withdrawal or worsening of RLS or emergence of other symptoms which will be

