managed clinically by physicians. If deemed appropriate for reasons related to safety, tolerability, and continuation of the study, the PI at his discretion may modify the tapering schedule of the DA although every attempt will be made to adhere to the protocol specified schedule of DA tapering. All subjects will continue to be on Horizant for the entire duration of this study with close follow up.

During each clinic visit all subjects will undergo careful evaluations (by a physician) that will include: medical history such as appearance of any new health problems, any new symptoms/adverse events between clinic visits, concomitant medication(s) history(medication reconciliation), physical examination with assessment of vital signs, ASRS, IRLS, RLS-QOL, and MOS-SS.

All subjects will undergo laboratory testing (CBC with Diff and CMP) during screening, on day 30 and day 360 (final clinic visit). In addition, urine sample will be collected at screen visit for illegal drug testing. Additional hematology and urine sample analysis for illegal drug will be performed as needed at the discretion of the investigators if an adverse event is reported by a subject. Serum Ferritin level will be performed as needed at the discretion of the investigators.

Urine pregnancy screening is required for all females of childbearing potential at screen and each clinical visits, if positive, serum pregnancy test will be performed. Female subjects who have undergone surgical sterilization, who are post-menopausal (defined as age >50 and >1 year of amenorrhea), who have medically documented ovarian failure (defined as age <50 with serum estradiol and follicle-stimulating hormone [FSH] levels within the institutional postmenopausal range and a negative serum or urine β HCG) do not need to undergo pregnancy screening.

Study Procedure

If you agree to be in this study, you will sign this form before any study tests are done. Talk with your study doctor before starting any new medicine. This includes medicines you buy at the drug store and herbal or dietary supplements (vitamins). Some drugs, as well as alcohol, use can cause serious side effects if taken with the study drug. Please ask your study doctor if you have any questions about the medicine(s) you are taking. He/she will tell you which medicine you cannot take during the study.

This study has four periods: screening, treatment and maintenance and follow-up.

Visit 1: Screening Period, (prior to treatment with study drug)

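### The dopaminergic taper starts at Day 90 with no contact scheduled until Day 120, so a cheap telephone check is missing while there is still dose left to hold

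*Protocol*

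**What the plan says.** Section 4 starts the taper at the Day 90 visit, which opens Rx Phase 2, and gives its rate: "all subjects will be tapered off (by 50% reduction in dose each week) of their current dopaminergic agent". Clinic visits follow on Days 120, 180 and 360. Section 6.1 repeats the taper and the visits.

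For the time after Day 90, section 4 states: "During this period all subjects will be monitored for symptoms of dopamine withdrawal or worsening of RLS or emergence of other symptoms". Such symptoms are to be managed by physicians. If safety or tolerability requires it, "the PI, at his discretion, may modify the tapering schedule of the DA", although the stated schedule is the default.

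The reason for caution is also given: "Abrupt withdrawal of DA agent can be potentially dangerous due to DA withdrawal symptoms including life-threatening Neuroleptic Malignant Syndrome". The two-phase design, with Horizant added first and DA tapered afterwards, is presented as the response to that risk.

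Other relevant provisions:
- The flow chart (section 3) and the visit list in section 6.1 have no entry between Day 90 (±14) and Day 120 (±14).
- Section 10.2 ties adverse-event enquiry to the visits.
- Section 11 gives subjects site telephone numbers, and section 11.2 makes the investigator responsible for monitoring and recording all adverse events.
- Section 8.9 requires withdrawal from the study for significant DA withdrawal effects, as judged by the investigator.

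**The concern.** Two safeguards depend on the site learning about symptoms during the taper: the PI's freedom to slow it, and the investigator's judgement under section 8.9. The schedule gives neither of them a planned source of information between Day 90 and Day 120, which is when the DA dose falls.

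If a subject does not volunteer symptoms, the first planned question comes when little or no DA is left to hold. Symptoms that have settled by Day 120 are recorded from recall. At stake are the timeliness of a safety decision and the quality of the record of withdrawal symptoms in the taper month.

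**Working it through.** The protocol gives no figure for the dose remaining at Day 120, so there is none to reproduce. The inputs are the taper start (Day 90 visit), the rate (50% per week) and the visit windows (±14 days at both Day 90 and Day 120).

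**Gap without a scheduled contact.** Nominal: 120 − 90 = 30 days. Shortest: (120 − 14) − (90 + 14) = 106 − 104 = 2 days. Longest: (120 + 14) − (90 − 14) = 134 − 76 = 58 days.

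**Dose removed by the next visit.** The text does not say whether 50% is of the current or the starting dose, nor whether the first cut falls at the visit or a week later, so each reading is shown. Let k be the number of weekly cuts in the gap: k = floor(gap/7) if the first cut comes a week after the visit, and one more if it comes at the visit. Halving the current dose removes 1 − 0.5^k. Cutting 50% of the starting dose removes min(1, 0.5k).

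| Gap | Halving, first cut a week later | Halving, first cut at visit | 50% of starting dose |
|---|---|---|---|
| 2 days | 0% (k = 0) | 50% (k = 1) | 0% or 50% |
| 16 days | 75% (k = 2) | 87.5% (k = 3) | 100% |
| 30 days (nominal) | 93.75% (k = 4) | 96.9% (k = 5) | 100% |
| 58 days | 99.6% (k = 8) | 99.8% (k = 9) | 100% |

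The nominal range is therefore 93.75% to 100% removed, or 6.25% to 0% left. If halving is stopped at an earlier step, the figure is 100%.

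**When DA reaches zero if cuts are of the starting dose.** Cuts on Days 90 and 97 reach zero on Day 97, which is 120 − 97 = 23 days before the visit. Cuts on Days 97 and 104 reach zero on Day 104, 16 days before.

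**What a call would find.** After the first cut and before the second, 1 − 0.5 = 50% of the dose is still in place on either reading. If cuts fall on Days 90 and 97, the call has to be made before the Day 97 reduction is taken.

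**Contact spacing.** The intervals from Day 0 are 30, 60, 30, 60 and 180 days. The interval shortens from 60 to 30 days when the taper starts, which equals the interval after Horizant is started.

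**The case against.** The strongest reply is that nothing promised is left undone. The monitoring sentence comes straight after the list of three clinic visits, and those visits, each with a physician taking an interval history, can fairly be read as the monitoring. No weekly contact is promised. Subjects can telephone, the investigator has a general duty on adverse events, the protocol speaks of close follow-up, and this is a single site with 50 subjects.

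That reply stands against four stronger readings that a reader might infer:
- *The protocol contradicts itself.* It does not. Monitoring at the visits is consistent with the text.
- *A life-threatening hazard goes unmonitored.* The warning concerns abrupt withdrawal, and the taper under Horizant cover is the stated mitigation.
- *Nobody asks about symptoms before Day 120.* The documents show only that no such contact is scheduled. They do not show that none takes place.
- *The schedule ignores the taper.* The visit interval halves at that point.

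The reply does not remove the timing problem. A telephone number depends on the subject using it, the general duty has no set time in this interval, and the Day 120 history is retrospective. On nominal dates all the scheduled information arrives after at least 93.75% of the dose has gone.

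**Conclusion.** The point holds as a modest, low-cost safety improvement. No enquiry about withdrawal or worsening RLS is scheduled while enough DA remains for slowing the taper to be a real option.

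The 93.75% to 100% figure assumes nominal dates and an unmodified taper. Across the visit windows the gap runs from 2 to 58 days. With a visit at 16 days, for example, 12.5% to 25% of the dose would remain under successive halving. The percentage describes dose, not harm. The protocol gives no rate of withdrawal symptoms, so the number of events caught late or missed cannot be estimated. The point applies to subjects who reach the taper, at most 50.

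**What to change.** In the flow chart and in sections 4 and 6.1, add two brief telephone safety contacts by existing staff:
1. One after the first dose cut and before the second cut is taken.
2. One about a week after the last DA dose.

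Time both from the subject's actual taper start, not from nominal study days. Use a short enquiry about withdrawal symptoms, worsening RLS and adverse events, record it in the CRF, and pass any positive answer to the physician. So that the calls can be placed, state whether 50% is of the current or the starting dose, and the step at which DA stops.

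The cost is 2 calls × up to 50 subjects = at most about 100 short calls. Under section 14.3 the amendment goes to the funder and then to the IRB for approval, and the consent form may need revision. No extra visits, tests or staff are needed.

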5. BACKGROUND

5.1 Study Rationale:

RLS is common condition that is usually treated with dopaminergic medications. Augmentation is the main complication during long-term DA treatment of RLS. It was first described in 1996 with overall increase in severity of RLS symptoms typically more severe than pre-dopaminergic therapy with earlier occurrence of symptoms and involvement of previously uninvolved extremities. It can be a very devastating experience in some patients. Augmentation is reported in up to 82% of people taking levodopa (Allen RP, Earley CJ. Augmentation of the restless legs syndrome with carbidopa/levodopa. Sleep 1996;19:205-13)

Features of Augmentation include earlier onset of RLS symptoms, increased severity of symptoms, reduced time before symptoms begin when resting, spread of symptoms to previously uninvolved body parts, and reduced effectiveness of medications including longer time before medication begins to work and less ability to decrease symptoms.

Augmentation severity can be assessed by a validated scale, ASRS, in these patients.

Management of Augmentation has not been studied in clinical trials. Presently, there is no approved medication (by FDA) to treat augmentation. In addition, currently, there are no specific practice guidelines as to how to treat augmentation. 'More research is needed to identify the optimal approach for treating augmentation once it develops. Sudden withdrawal of the offending dopaminergic drug does not appear to be a well-tolerated strategy' (Kurlan. Journal of Parkinsonism & Restless Legs Syndrome Vol 3, 49-52, 2013).

Pubmed search (conducted in Jan 2015, with key words "Horizant, Augmentation") revealed several articles (see attachments) suggesting that Horizant is the only FDA approved Nondopaminergic drug used in the treatment of RLS, with predictable bioavailability, acceptable safety profile and with any reports of augmentation. Therefore, we suggest that Horizant may be a best-suited drug to treat augmentation in RLS patients. Thus, we propose to conduct a clinical drug trial to examine Horizant in RLS patients who developed augmentation.

Abrupt withdrawal of DA agent can be potentially dangerous due to DA withdrawal symptoms including life-threatening Neuroleptic Malignant Syndrome. Therefore, to improve subject tolerability and minimize DA withdrawal, we have designed this clinical trial into 2 phases: Rx Phase 1 and Rx Phase 2 (described below)

6. Objectives:

The Primary objective: is to evaluate the efficacy of Dopamine combined therapy with addition of Horizant (600mg, oral, once daily) for 90 days in the treatment of Augmentation.

The Secondary objectives: is to evaluate the efficacy of Horizant (600 mg, oral, once daily) alone with Dopaminergic (DA) taper for up to 270 days in the treatment of Augmentation.

6.1 Study Design:

This is an Open label Single arm study. The purpose of the study is to demonstrate the efficacy of Horizant in patients with RLS who exhibit augmentation while on Dopaminergic therapy. Adult patients (age 18-85 years) with diagnosis of primary RLS (diagnosed by study investigators) with augmentation on dopaminergic therapy will be screened for participation in the study. RLS diagnosis will be made by the study investigators using International RLS study group criteria. Patients with augmentation on dopaminergic therapy as defined by NIH 2007 (refer to attachment) with ASRS of 5 to 15 will be offered to participate in the study. Inclusion and exclusion criteria are listed below. The study will be performed after approval of the Institutional Review Board of the University of Missouri.

A total of 50 subjects will be entered into the study over a period of 1 year. Written consent will be obtained from all patients. After pre-participation evaluation for eligibility, subjects will be selected and enrolled in the study and followed for a total of 6 follow up visits (Days 0, 30, 90, 120, 180, 360). Subjects Enrollment period will last up to 12 months. The total duration of study is 36 months.

There is no report of Augmentation due to Horizant use in the literature to this date. Therefore, initially Horizant (600 mg oral once daily at 5 pm) will be added on as an adjunct to all subjects' along with stable dose of their current dopaminergic (DA) agent and both medications will be continued for a total period of 90 days from day 0 to day 90.

At the 90th day follow-up visit, while maintaining the same dose of Horizant, all subjects will be tapered off (by 50% reduction in dose each week) of their current dopaminergic agent. Subsequently all subjects will be followed for additional three follow up clinic visits (days 120, 180, 360). During this period all subjects will be monitored for symptoms of dopamine withdrawal or worsening of RLS or emergence of other symptoms which will be

managed clinically by physicians. If deemed appropriate for reasons related to safety, tolerability, and continuation of the study, the PI at his discretion may modify the tapering schedule of the DA although every attempt will be made to adhere to the protocol specified schedule of DA tapering. All subjects will continue to be on Horizant for the entire duration of this study with close follow up.

During each clinic visit all subjects will undergo careful evaluations (by a physician) that will include: medical history such as appearance of any new health problems, any new symptoms/adverse events between clinic visits, concomitant medication(s) history(medication reconciliation), physical examination with assessment of vital signs, ASRS, IRLS, RLS-QOL, and MOS-SS.

All subjects will undergo laboratory testing (CBC with Diff and CMP) during screening, on day 30 and day 360 (final clinic visit). In addition, urine sample will be collected at screen visit for illegal drug testing. Additional hematology and urine sample analysis for illegal drug will be performed as needed at the discretion of the investigators if an adverse event is reported by a subject. Serum Ferritin level will be performed as needed at the discretion of the investigators.

Urine pregnancy screening is required for all females of childbearing potential at screen and each clinical visits, if positive, serum pregnancy test will be performed. Female subjects who have undergone surgical sterilization, who are post-menopausal (defined as age >50 and >1 year of amenorrhea), who have medically documented ovarian failure (defined as age <50 with serum estradiol and follicle-stimulating hormone [FSH] levels within the institutional postmenopausal range and a negative serum or urine β HCG) do not need to undergo pregnancy screening.

Study Procedure

If you agree to be in this study, you will sign this form before any study tests are done. Talk with your study doctor before starting any new medicine. This includes medicines you buy at the drug store and herbal or dietary supplements (vitamins). Some drugs, as well as alcohol, use can cause serious side effects if taken with the study drug. Please ask your study doctor if you have any questions about the medicine(s) you are taking. He/she will tell you which medicine you cannot take during the study.

This study has four periods: screening, treatment and maintenance and follow-up.

Visit 1: Screening Period, (prior to treatment with study drug)

Before you begin taking study drug, subject will need to have the following tests to find out if you can be in the study.

- Medical history: We will ask about your health and any illnesses and any medicines you are taking or have taken within the last 30 days (including over-the-counter medicine, vitamins or herbal supplements and how much caffeine you use weekly).
- We will ask you about your current and prior Augmentation treatment, symptoms, your usual bedtime and awakening times.

- You and the staff will complete assessments on how you are feeling and if you have any thoughts about harming yourself.
- Physical examination: You will have a full physical examination including neurological exam, height and weight.
- Vital signs: You will have your temperature, heart rate, blood pressure, temperature and breathing rate collected.
- Urine testing: You will collect a sample of urine for illegal drug screening and pregnancy testing.
- Blood testing: We will collect blood samples (2 teaspoons or~10ml) for lab tests including hematology. Additional blood sample (~1/4 of teaspoon or 1.25ml) will be collected if you are a woman and your urine pregnancy test turn positive.
- Augmentation severity rating scale (ASRS) 3 item questionnaire to evaluate the severity of your augmentation symptom.
- International restless legs syndrome-rating scale (IRLS) a way to measure severity of your symptoms.
- If you are a woman and can have children you must use a medically acceptable method of contraception which can include estrogen-progestin oral contraceptive pills, patches, or vaginal ring (if one of these methods is chosen it must have been used consistently for 2 months prior to the first dose of study drug); progestin implant or injection; diaphragm with spermicide; male condom plus vaginal spermicide; surgical sterilization; intrauterine device; vasectomy of the partner or spouse (>6 months prior to baseline).
- If you are a man, you should not father children while in the study. Your study doctor will talk to you about either agreeing to use specific methods of birth control or agreeing to abstain from sexual intercourse during the study and for 30 days after study completion.
- We will instruct you on how to discontinue any medications not allowed while you are in the study. Without your regular medications, your medical conditions or symptoms may get worse however, we will check with the doctor that prescribed the medication to make sure that it is safe for you to stop taking it. You might not be able to drive or operate machinery. If your medical conditions or symptoms do get worse, please call the study doctor at the phone number provided in this consent form.
- We will make an appointment for you to return for Visit 2 (baseline visit), within the next 15 days or less.

Visit 2 (day 0+/-7), visit 3 (day 30+/-7), visit 4 (day 90+/-14), visit 5 (day 120+/-14), visit 6 (day 180+/-14) and visit 7 (day 360+/-14) will have the following tests and procedures except that visit 2, 4, 5 and 6 will not have blood sample collection.

- Medical history: We will ask about your health and any illnesses and any changes in medicines you are taking or have taken since last visit.
- We will ask you about your current and prior Augmentation treatment, symptoms, your usual bedtime and awakening times.
- You and the staff will complete assessments on how you are feeling and if you have any thoughts about harming yourself.
- Physical examination: You will have a full physical examination including neurological exam, height and weight.

- Vital signs: You will have your temperature, heart rate, blood pressure, temperature and breathing rate collected.
- Blood testing: We will collect blood samples (2 teaspoon or~10ml) for lab tests including hematology. Additional blood sample (~1/4 of teaspoon or 1.25ml) will be collected if you are a woman and your urine pregnancy test turn positive.
- Urine testing: You will collect a sample of urine for pregnancy testing.
- Augmentation severity rating scale (ASRS) 3 item questionnaire to evaluate the severity of your augmentation symptom.
- International restless legs syndrome-rating scale (IRLS) a way to measure severity of your symptoms.
- Restless legs syndrome-quality of life (RLS-QOL) a way to measure improvement in quality of your life.
- Medical outcome study-sleep scale (MOS-SS) a way to assess your sleep.

Blood sample collection: a blood sample (2 teaspoon or \sim 10ml) will be collected for complete blood count with differential and comprehensive metabolic panel at screening visit, visit 3 (day 30) and visit 7 (Day 360). In addition, it will be performed as needed at the discretion of the investigators if an adverse events is reported by a subjects. In other words, if a side effect occurs and the investigator feels additional tests will be helpful, then it will be done. Additional blood sample (\sim 1/4 of teaspoon or 1.25ml) will also be collected if urine pregnancy test turn positive. Serum Ferritin level will be performed as needed at the discretion of the investigators. The total amount of blood sample collected will be 6-7 teaspoon or 30-35ml for the entire study.

7. STUDY POPULATION:

7.1 Number of Subjects: 50 (we believe that we will be able to recruit only 50 eligible subjects during the one year enrollment period)

7.2 Inclusion Criteria:

To be eligible for entry into this study, candidates must meet **all** of the following eligibility criteria before enrollment:

- 1. Adult patients with diagnosis of RLS for more than one year.
- 2. Patients who are on DA therapy for 6 months or longer.
- 3. Patients who developed Augmentation (on stable dose of DA) lasting for 3 months or longer.
- 4. Augmentation severity rating scale of 5 to 15.
- 5. Both males and females
- 6. Age range = 18-85 year

7.3 Exclusion Criteria:

Candidates will be excluded from study entry if **any** of the following exclusion criteria exist at the time of screening phase.

Patients who have history of:

- Known Hypersensitivity to Horizant or Gabapentin products
- o Peripheral neuropathy
- o Radiculopathy
- o Peripheral vascular disease
- o Uremia (abnormal BUN or Creatinine on CMP)
- o Anemia
- o Patients who are currently pregnant
- Patients who currently take opioids, lithium, anti-nausea medications (e.g. metoclopramide), dopaminergic antagonists (e.g. Haloperidol), 1st generation antihistamines (e.g. diphenhydramine, pseudoephedrine), anti-psychotic medications and iron therapy.
- o Subjects with impaired decision making capability.
- 7.4 Medical History Exclusions: as per Exclusion criteria
- **7.5 Treatment History Inclusions or Exclusions**: as per Inclusion and Exclusion criteria
- **7.6 Miscellaneous :** Not applicable
- 7.7 Screening Log: will be maintained

Participating center is required to document all screened candidates initially considered for inclusion in this study and to specifically state the reason(s) for their exclusion

